10. INVESTIGATIONAL DEVICE

10.1 DEVICE NAME

Excimer Laser Coronary Atherectomy (ELCA[®]) Products

Excimer Laser Coronary Atherectomy (ELCA[®]): Coronary Laser Atherectomy Catheters (OTW and RX)

Mode of Application: Invasive

Stand-alone modality or in conjunction with Percutaneous Transluminal Coronary Balloon Angioplasty (PTCA)

Coronary Laser Atherectomy Catheters (Over-The-Wire [OTW] and Rapid Exchange [RX])

10.2 MODELS:

- 110-001 ELCA 0.9mm Extreme OTW Laser Catheter
- 110-002 ELCA 0.9mm 80 Hz Extreme OTW Laser Catheter
- 110-003 ELCA 0.9mm Vitesse RX Laser Catheter
- 110-004 ELCA 0.9mm 80 Hz Extreme RX Laser Catheter
- 114-009 ELCA 1.4mm Vitesse RX Laser Catheter
- 117-016 ELCA 1.7mm Vitesse RX Laser Catheter
- 120-009 ELCA 2.0mm Vitesse RX Laser Catheter
- 117-205 ELCA 1.7mm Vitesse-E RX Laser Catheter
- 120-008 ELCA 2.0mm Vitesse-E RX Laser Catheter

ELCA products are percutaneous, single use, disposable medical devices designed for excimer laser coronary atherectomy within native coronary arteries and saphenous vein bypass grafts (SVG). ELCA products are typically employed, as a precursor treatment or in conjunction with percutaneous transluminal coronary angioplasty (PTCA) or percutaneous coronary intervention (PCI) techniques that employ balloon catheter dilatation and/or stenting, to reduce, minimize or alleviate flow-limiting stenoses or occlusions following placement of a guidewire across the target treatment site.

ELCA products are approved for use in conjunction with the Spectranetics CVX-300[®] Excimer Laser System (CVX-300) and are intended for use in patients with single or multivessel coronary artery disease (CAD) or SVG disease as a stand-alone modality or in conjunction with PCI techniques.

[figure not shown]

Figure 2: ELCACatheter

Figure 2: CVX-300 Excimer Laser

10.3 INDICATIONS FOR USE

ELCA products are typically employed as a precursor interventional treatment for patients presenting with a variety of obstructive CAD and SVG indications (e.g., complex lesion patterns, subtotal and total occlusions, small vessel disease, resistant lesions, acute thrombosis) and a range of comorbid conditions (e.g., coronary insufficiency, acute coronary syndrome, acute myocardial infarction, heart failure, arrhythmia).

ELCA indications for use are based on lesion, stenosis and/or occlusion physical descriptors versus the clinical presentation of the patient. The ELCA indications are identical for CE mark (EU) and FDA (US) product labeling. The current indications include;

- Occluded saphenous vein bypass grafts
- Ostial lesions
- Long lesions - (greater than 20 mm in length)
- Moderately calcified stenoses - (Heavily calcified stenoses are those lesions that demonstrate complete calcification when identified under fluoroscopy by angiography prior to the procedure. Moderately and slightly calcified stenoses are all others.)
- Total occlusions traversable by a guidewire

Spectranetics Corporation

Study Protocol Number: ELCA-1016

Version 1.0

Dated: 12 Oct 2016

- Lesions which previously failed balloon angioplasty - (This includes those lesions that were treated unsuccessfully by PTCA. Lesions that have undergone a complicated PTCA procedure are not included in this category.)
- ONLY ELCA, NOT ELCA X-80: Restenosis in 316L stainless steel stents, prior to the administration of intravascular brachytherapy.

Contraindications

- Lesion is in an unprotected left main artery.
- Lesion is beyond acute bends or is in a location within the coronary anatomy where the catheter cannot traverse.
- Guidewire cannot be passed through the lesion.
- Lesion is located within a bifurcation.
- Patient is not an acceptable candidate for bypass graft surgery.

[figure not shown]

Figure 1: Over the Wire

Table 1.1 ELCA® Coronary Laser Atherectomy Catheter Models

Device Description	Model Number	Max. Guidewire Compatibility (in.)	Max. Tip Diameter (in.)	Max. Tip Diameter (mm)	Sheath Compatibility (Fr)	Working Length (cm)
OTW Catheter Specifications						
0.9 mm	110-001	0.014	0.038	0.97	4	135 ± 5

Glossary of Special Terms

Antegrade Fashion = In the direction of blood flow.

Baseline Angiography = Record of the cardiac muscle and blood vessels prior to a given interventional angioplasty procedure.

Retrograde Fashion = In the direction opposite to blood flow.

[figure not shown]

Figure 2: Rapid Exchange Eccentric

Figure 3: Rapid Exchange

Device Description	Model Number	Max. Guidewire Compatibility (in.)	Max. Tip Diameter (in.)	Max. Tip Diameter (mm)	Sheath Compatibility (Fr)	Working Length (cm)
RX Catheter Specifications						
0.9 mm	110-003	0.014	0.038	0.97	4	135 ± 5
1.4 mm	114-009	0.014	0.057	1.45	5	135 ± 5
1.7 mm	117-016	0.014	0.069	1.75	6	135 ± 5
1.7 mm E	117-205	0.014	0.065	1.65	6	135 ± 5
2.0 mm E	120-008	0.018	0.079	2.0	7	135 ± 5
2.0 mm	120-009	0.014	0.080	2.0	7	135 ± 5

10.4 DEVICE FAILURE/ MALFUNCTIONS

In case of device failure or malfunction, Investigator should attempt again with the new study device to treat the target lesion.

All failures and malfunctions of the study device must be sent to the CRO/Sponsor, preferably within 24 hours of knowledge of the event. The investigator must return any damaged study device to the Sponsor with an explanation of why the study device was opened but unused. All device failure and malfunctions will be reported in the Clinical Study Report.

10.5 DEVICE SUPPLY & DEVICE LABELING

Where applicable, the investigational device and its associated components will have a label according to ISO14155 (current version) that will be visible on the pertinent shipping cartons and storage containers. The required labels or instructions for use (IFU) will bear the following information:

- Name, model and lot number of the Excimer Laser Coronary Atherectomy (ELCA[®]) Products
- Name and addresses of the manufacturer and distributor
- Labeling statement: “FOR CLINICAL INVESTIGATION ONLY”
- Quantity of contents

Spectranetics Corporation

Study Protocol Number: ELCA-1016

Version 1.0

Dated: 12 Oct 2016

- All relevant contraindications, hazards, adverse device effects, interfering substances or devices, warnings and precautions
- Expiration date

10.6 DEVICE STORAGE

Store according to *Instruction for Use*, the study device has to be stored in a cool, dark and dry location at maximum temperature of 25 °C.

10.7 DEVICE ACCOUNTABILITY

Access to investigational devices shall be controlled and the investigational devices shall be used only in the clinical investigation and according to the CIP.

The sponsor or designee shall keep records to document the physical location of all investigational devices from shipment of investigational devices to the investigation sites until return or disposal. The principal investigator or an authorized designee shall complete the Investigational Device Accountability Log in order to keep records of the receipt, use, return and disposal of the investigational devices, which shall include:

- Date of receipt
- Identification of each investigational device (batch/serial number or unique code)
- Expiry date, if applicable
- Date or dates of use
- Subjects identification code, if applicable
- Date on which the investigational device was returned/explanted from subjects, if applicable
- Date of return of unused, expired or malfunctioning investigational devices, if applicable

11. RISK BENEFITS EVALUATIONS

The risk assessment, to support the safety of Excimer Laser Coronary Atherectomy (ELCA[®]) Product are documented in the previous clinical evaluations of the device. Study subjects will be informed of all known potential side effects and complications associated with study treatment and evaluations prior to enrollment in the study.

The treatment will be performed according to routine hospital practice. Excimer Laser Coronary Atherectomy (ELCA[®]) Product is CE mark approved.

No patient identifier information will be collected during the study. Each patient will be assigned a unique identifier via Remote Data Capture system. This information is then pooled with all the data for analysis and reporting.

The risks of using this device in coronary lesions may be similar to risks encountered with other marketed stainless steel stents/drug eluting stents/ atherectomy catheter. Excimer Laser Coronary Atherectomy (ELCA[®]) Product is not commercially available in Indian market for its use. Information about risk and risk mitigation may include, but is not limited to;

- **Cardiac events:**

Myocardial infarction or ischemia, abrupt closure of coronary artery, restenosis of treated artery (greater than 50% obstruction), cardiogenic shock, angina, tamponade, perforation or dissection of coronary artery or aorta, cardiac perforation, emergency cardiac surgery, pericardial effusion, aneurysm formation.

- **Arrhythmic events:**

Ventricular tachycardia, ventricular fibrillation, atrial fibrillation, bradycardia.

- **Respiratory events:**

Acute pulmonary edema, congestive heart failure, respiratory insufficiency or failure.

- **Vascular events:**

Access site hematoma, hypotension/hypertension, pseudoaneurysm, arteriovenous fistula formation, retroperitoneal hematoma, vessel dissection or perforation, thrombosis or occlusion, compromise of side branch patency, vasospasm, peripheral

ischemia, dissection, distal embolization (air, tissue debris, thrombus).

- **Neurologic events:**

Permanent (stroke) or reversible (TIA) neurologic event, femoral nerve injury, peripheral nerve injury.

- **Bleeding events:**

Access site bleeding or hemorrhage, hemorrhage requiring transfusion or other treatment. Allergic reactions to contrast media, antiplatelets, anticoagulants, to the drug carrier (PLLA), to Sirolimus and/or Magnesium, Yttrium, Neodymium, Zirconium, Gadolinium and Dysprosium.

- **Infection and sepsis.**

- **Death.**

The following complications may be associated with the use of coronary stenting devices or PTCA:

- Allergic reaction to contrast medium
- Bleeding complications
- Cardiac tamponade
- Cerebrovascular accident
- Dissection of coronary artery
- Drug reactions to antiplatelet agents, anticoagulation agents and/or contrast media
- Emboli, distal (tissue, air or thrombotic emboli)
- Endocarditis
- Failure to deliver the required therapy
- Fever
- Hematoma
- Hemorrhage
- Injury of the coronary artery
- Pain and tenderness
- Pyrogenic reaction
- Renal failure
- Emergency CABG

Based upon the existing experience with the Excimer Laser Coronary Atherectomy (ELCA[®]), it can be concluded that the risks associated with the use of the ELCA[®] are acceptable under the conditions outlined in this study protocol, and that the potential benefits may outweigh the risks.

Moreover, subjects will be monitored closely throughout the clinical investigation duration.

Spectranetics Corporation

Study Protocol Number: ELCA-1016

Version 1.0

Dated: 12 Oct 2016

Subjects will be evaluated clinically at pre-determined time points to assess their clinical status till the end of study.

Potential Benefits

Participation in this study is voluntary. Subjects potentially could benefit through the procedure of study device, as compared to the routine angioplasty for the patient population under consideration in this study. As already mentioned, several studies have shown the benefits of standalone ELCA atherectomy and ELCA atherectomy with stent implantation has better patient outcome in similar patient population. Information gathered from this study will help confirm the safety and performance of the Excimer Laser Coronary Atherectomy (ELCA[®]) in subjects with coronary artery disease (CAD).

12. CLINICAL INVESTIGATION

12.1 STUDY DESIGN

This is a Prospective, Open label, Non-randomized, Single-Arm, Multicenter Study to Evaluate the Procedural Safety and Efficacy of ELCA[®] in Treatment of Patients with Single or Multivessel Coronary Artery Disease (CAD).

12.2 STUDY POPULATION

Up to 30 patients will be enrolled at up to 05 Indian study sites. Patients will be followed from enrollment through 30 days \pm 7 days for the effectiveness and safety endpoints at the study centre.

The center's compliance to the clinical investigation plan will be assessed on an ongoing basis. In case of serious non-compliance, the sponsor may decide to stop patient enrollment in a center based on its assessment

12.3 STUDY DURATION

Duration of this clinical study is up to 12 months which includes trial set-up, enrollment period, study procedures, follow-up visits, data analysis and release of the clinical study report.

Study will start upon the receipt of the central Indian regulatory authority's approval as well as Ethics Committee approval at respective sites. Up to 30 eligible subjects will be enrolled in the study. All subjects will be followed clinically until one month (30 \pm 7 days), post-procedure.

12.4 STUDY OBJECTIVES

Primary Objective

To evaluate the safety and efficacy of ELCA[®] in patients with single or multivessel CAD either as a stand-alone modality or in conjunction with Percutaneous Transluminal Coronary Balloon Angioplasty (PTCA).

Secondary Objectives:

- To determine post-procedural TIMI Flow grade
- Lesion Morphology
- Device-related complications
- Procedure-related complications

12.5 STUDY ENDPOINTS

Efficacy Endpoint:

- Device Success: Successful crossing of the ELCA Catheter across the entire length of the stenotic lesion
- Procedural Success: Target lesions with less than 50% residual stenosis after laser and adjunctive therapy

Safety Endpoint:

- Freedom from major adverse cardiac events (MACE) through hospital discharge and at one month
MACE is defined as Death, Non-Q-wave and Q-wave myocardial infarction (MI), Target Lesion Revascularization, Cardiac Tamponade and Life-threatening arrhythmias
- TIMI Flow
- Lesion Morphology
- Device-related complications
- Procedure-related complications

In order to fully characterize the procedure, information of all treated lesions will be collected irrespective of whether the lesion has been treated with ELCA[®] product.

Electronic Case Report Forms will be utilized to collect relevant information.

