6. STUDY SYNOPSIS

Title	A Prospective, Open label, Non-randomized, Single-Arm, Multicenter Study to Evaluate the Procedural Safety and Efficacy of ELCA [®] in Treatment of Patients with Single or Multivessel Coronary Artery Disease (CAD).
Trial Location	India
Name of the Sponsor	Spectranetics Corporation
Protocol Number	ELCA-1016
Development phase	III
Name of study device	Excimer Laser Coronary Atherectomy (ELCA [®]): Coronary Laser Atherectomy Catheters (OTW and RX) Mode of Application: Invasive Stand-alone modality or in conjunction with Percutaneous Transluminal Coronary Balloon Angioplasty (PTCA)
Indication	Single or Multi vessel Coronary Artery Disease (CAD)
Objective	
Primary Objective: To evaluate the safety and efficacy of ELCA[®] in patients with single or multivessel CAD either as a stand-alone modality or in conjunction with (PTCA),
 
Secondary Objectives:
 
 • To determine post-procedural TIMI Flow grade • Lesion Morphology • Device-related complications • Procedure-related complications
Study Endpoints	
Efficacy Endpoint:
 
 • Device Success: Successful crossing of the Laser Catheter across the entire length of the stenotic lesion • Procedural Success: Target lesions with less than 50% residual stenosis after laser and adjunctive therapy.

Spectranetics Corporation

Study Protocol Number: ELCA-1016

Version 1.0

Dated: 12 Oct 2016

	
Safety Endpoint:
 
 • Freedom from Major Adverse Cardiac Events (MACE) through hospital discharge and at one month. MACE is defined as Death, Non-Q-wave and Q-wave myocardial infarction (MI), Target Lesion Revascularization, Cardiac Tamponade and Life-threatening arrhythmias • TIMI Flow • Lesion Morphology • Device-related complications • Procedure-related complications 	
Device Failure/ Malfunctions	All failures and malfunctions of the study device must be sent to the CRO/Sponsor, preferably within 24 hours of knowledge of the event.	
Study design	Prospective, Open label, Non-randomized, Single-arm, Multicenter study.	
No. of centers	Total 05 sites in India. The center's compliance to the clinical investigation plan will be assessed on an ongoing basis. In case of serious non-compliance, the sponsor may decide to stop patient enrollment in a center based on its assessment.	
Sample Size	30	
Screening & Follow Up	Screening	Day -10 to 0
	Baseline (study procedure)	Day 0

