As opposed to the mandatory fissuring and cracking of the plaque and over distending the arterial wall using conventional coronary angioplasty¹⁰, laser atherectomy might have the theoretical potential of reducing complications and probably as a result of reduced injury, of decreasing the incidence of restenosis.

LASER is an acronym for Light Amplification by Stimulated Emission of Radiation. Although the history of laser begins in 1951, the first medical application is reported by Goldman in 1962 and used in 1963 for the experimental ablation of atherosclerotic plaques. The first clinical applications were performed by Choy and Ginsburg in 1983.

[figure not shown]

Figure 1: ELCA[®] Mode of Action

Spectranetics Corporation

Study Protocol Number: ELCA-1016

Version 1.0

Dated: 12 Oct 2016

Excimer Laser Coronary Atherectomy (ELCA[®]) uses the high energy, monochromatic light beam to alter or dissolve (vaporize) the plaque without damaging the surrounding tissue. Fiber-optic catheters are used to deliver this light beam. For endovascular applications, Xenon Chloride excimer laser is used and its fiber-optic catheter has multiple small fibers, rather than just a few large fibers, in order to be flexible enough to navigate in the arterial tree.

Laser can be used in both coronary and peripheral applications. In coronaries, excimer laser can be used to remove thrombi; to vaporize pro coagulant reactants in addition to debulking the underlying plaque; and to facilitate stent delivery. In the CARMEL multicenter study, excimer laser angioplasty was successfully used in more than 90% of the enrolled 151 acute myocardial infarction (AMI) patients with a large thrombus burden with a relatively low rate (8.6%) of major cardiac adverse events (MACE). It has been also used for in-stent restenosis: in the Laser Angioplasty for Restenotic Stents multicenter registry (LARS), laser angioplasty reduced 30-day repeat-target-site coronary intervention, but it did not decrease in 1 year. Balloon-resistant lesions, chronic total occlusions, calcified lesions, and under expanded stents in calcified lesions are some other scenarios in which excimer laser coronary atherectomy can be successfully used.

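### Does Procedural Success wrongly credit ELCA when a lesion was lased but not crossed and then opened by balloon or stent?

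*Protocol*

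**What the plan says.** Section 12.5 lists two efficacy endpoints, and the synopsis in Section 6 gives the same pair. The first concerns the catheter: "Device Success: Successful crossing of the Laser Catheter across the entire length of the stenotic lesion". The second concerns the final angiographic result: "Procedural Success: Target lesions with less than 50% residual stenosis after laser and adjunctive therapy". Neither is made a condition of the other.

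Section 12.4 sets the primary objective as the safety and efficacy of ELCA used alone or together with balloon angioplasty (PTCA). Section 10.2 describes the catheters as typically used before or alongside balloon dilatation and/or stenting. Section 9 gives the laser's coronary uses as removing thrombus and vaporizing procoagulant reactants, "in addition to debulking the underlying plaque; and to facilitate stent delivery".

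Section 12.5 adds that, to characterize the procedure fully, "information of all treated lesions will be collected irrespective of whether the lesion has been treated with ELCA". Section 16.3 requires the intervention report, lesion characteristics and all angiographies as source data, and Section 16.4 puts all study data in the electronic case report form.

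Section 15 derives the sample size from a regulatory recommendation of at least 25 patients plus 5 dropouts. The protocol states no expected success rate, performance goal, significance level or power.

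**The concern.** In a single-arm study no control rate separates what the laser did from what the balloon or stent did. The reader depends on the endpoint definitions for that. If the catheter fails to cross and the operator then opens the lesion by other means, the case counts as a Procedural Success although the device did not do what Device Success asks of it. The headline rate could then look better than the device's own performance.

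Two further points sharpen the worry. Two separate percentages do not show how many lesions were both crossed and opened. And a lesion that received no laser energy might slip into the count, since Section 10.4 speaks of a returned device "with an explanation of why the study device was opened but unused" and Section 12.5 collects data on lesions not treated with ELCA. At stake would be the interpretation of the efficacy result in a bridging study of 30 patients.

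**Working it through.** **The plan's own figure.** 25 recommended + 5 dropouts = 30, as stated in Section 15. No success rate enters this sum, so the wording of the endpoint cannot affect the sample size.

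**How each type of lesion is scored.** Applying the two definitions to target lesions that received laser:

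| Catheter crossed entire lesion | Final stenosis below 50% | Device Success | Procedural Success |
|---|---|---|---|
| yes | yes | yes | yes |
| yes | no | yes | no |
| no | yes | no | yes |
| no | no | no | no |

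The third row is the disputed one. It is scored as a failure on the device endpoint and a success on the procedure endpoint, and both statements are true of that lesion. The four rows carry four different pairs of scores, so the lesion-level data identify every case.

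**Lesions without laser.** The definition asks for the result after laser *and* adjunctive therapy, so a lesion with no laser does not meet it. The sentence in Section 10.4 concerns the return of a damaged catheter to the sponsor. The same section tells the investigator to try again with a new study device. It describes an unused catheter, not a lesion that went without laser and was then scored. The collection of data on other lesions in Section 12.5 is given a descriptive purpose and does not change the endpoint.

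**Size of the disputed cell.** Let d be the crossing rate and b the rate at which balloon or stent brings an uncrossed lesion below 50% stenosis. The share opened without crossing is (1 − d) × b. Neither value is in the protocol; both are assumed, with one lesion per subject and 30 lesions.

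| d | b = 0.30 | b = 0.95 | Lesions of 30 |
|---|---|---|---|
| 0.95 | 0.05 × 0.30 = 1.5 points | 0.05 × 0.95 = 4.8 points | 0.5 to 1.4 |
| 0.90 | 0.10 × 0.30 = 3.0 points | 0.10 × 0.95 = 9.5 points | 0.9 to 2.9 |
| 0.85 | 0.15 × 0.30 = 4.5 points | 0.15 × 0.95 = 14.3 points | 1.4 to 4.3 |

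These are ceilings for two reasons. They include uncrossed lesions that were never lased, which the definition excludes. They also give no credit where partial lasing helped the balloon or stent. Section 10.3 contraindicates a lesion in a "location within the coronary anatomy where the catheter cannot traverse", which makes a high d more plausible but does not guarantee it.

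For scale, the exact 95% (Clopper-Pearson) interval for 27 of 30 runs from 73.5% to 97.9%, a width of 24.4 points. Even the largest ceiling in the table is narrower than that.

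**What two totals leave open.** With D lesions crossed and P opened out of n, the number both crossed and opened lies between max(0, D + P − n) and min(D, P).

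- D = P = 27, n = 30: from 27 + 27 − 30 = 24 to 27, that is 80% to 90%.
- D = P = 28, n = 30: from 28 + 28 − 30 = 26 to 28, that is 86.7% to 93.3%.

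The range is real for a reader who is shown only the two totals. The study itself loses nothing, because both endpoints are assessed lesion by lesion and the joint count is a simple tabulation.

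**Would a joint rate isolate the laser?** Write c for the rate of final stenosis below 50% among crossed lesions. The joint rate is d × c; for example, with assumed d = 0.90 and c = 0.95 it is 0.855. But c is also measured after balloon or stent. A lesion that was crossed, stayed tight and was then stented counts in full. Requiring crossing lowers the number without removing the adjunct's contribution, so the joint rate could not be labelled the effect of ELCA either.

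**The case for a change.** The strongest case for the concern starts from the text, and on the text it is right: no section ties Procedural Success to crossing or says in words how an uncrossed lesion is scored. Failed crossings are foreseeable. Inclusion criterion 4 (Section 13.3) requires calcification or a chronic total occlusion without an upper limit on calcification. The contraindication for sites the catheter cannot reach is not among the exclusion criteria in Section 13.4 and applies only through use according to the instructions (Section 13.8). Adjunctive therapy is left open: the objective names balloon angioplasty, while Section 10.2 also mentions stents. And since the endpoint is fixed in the protocol, one may say that the analysis plan should not have to repair it.

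The literal reading stands, and so does the point that a cross-tabulation would be informative and cheap. What does not follow is that the definition is wrong. Nothing in it needs repair: an endpoint named for the procedure and worded to include adjunctive treatment measures just that, and the failed crossing is reported beside it. Showing the two endpoints jointly adds a summary of data already collected and changes no definition. That is what a protocol commonly leaves to the statistical analysis plan, which is not at hand here.

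**Conclusion.** The concern does not hold. Device Success and Procedural Success are two openly separate measures, one of the catheter and one of the whole procedure, and the second matches an objective that includes ELCA together with PTCA. Following the plan as written gives no wrong rate, and no decision rule in the protocol depends on either rate. The wording on laser already keeps unlased lesions out.

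The disputed cell is at most 0.5 to 1.4 of 30 lesions at an assumed 95% crossing rate and 1.4 to 4.3 at an assumed 85%. Both ranges rest on an assumed 30% to 95% success of balloon or stent and on one lesion per subject, although the study admits multivessel disease. The conclusion does not depend on these figures: even where the cell is larger, those lesions appear as failures on the device endpoint. What remains is a preference for one additional table, not a fault in the protocol.
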